<sup>8 Imaging is performed at the end of Cycle 4 and then at the end of every fourth cycle of treatment (end of Cycle 8, 12, 16, etc.). Exception: if a patient has PD yet continues protocol treatment, the next imaging should take place two cycles after the imaging showing PD. If that patient continues on protocol treatment, imaging should then take place every 4 cycles.

<sup>10 Blood draw for immune monitoring will be collected prior to the start of Cycles 1-5 and prior to the start of each post-imaging cycle thereafter (prior to Cycle 9, 13, 17, etc.)

<sup>11 In addition to the research blood collection on Day 1, research blood will be collected as per Section 14 on Cycle 2, Days 2-5. The collection on Cycle 2, Day 2 should take place 2-4 hours after completion of cryoablation and mDC therapy.

<sup>12 Tumor biopsies will be performed immediately prior to cryoablation on Cycle 2 Day 1 or 2 and Cycle 3 Day 1 or 2

<sup>13 Tumor biopsies will be performed at the end of Cycle 4 after radiologic evaluation

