# **11.0** Treatment Evaluation

# 11.1 Treatment evaluation using RECIST 1.1 guidelines

The first scan after treatment initiation will be performed at the completion of Cycle 4; scans will be then performed at the completion of every fourth cycle of treatment until disease progression is confirmed or withdrawn of consent. If a patient experiences PD yet continues protocol treatment, the next imaging should take place 2 cycles after the imaging showing PD. If that patient continues on protocol treatment, imaging should then take place every 4 cycles (See Section 4.0).

Disease progression for this protocol is defined as meeting the RECIST criteria for disease progression on two consecutive evaluations at least 6 weeks apart.

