    - ii. If the positive FDG-PET at follow-up is not confirmed as a new site of disease on CT at the same evaluation, additional follow-up CT scans (i.e., additional follow-up scans at least 4 weeks later) are needed to determine if there is truly progression occurring at that site. In this situation, the date of PD will be the date of the initial abnormal PDG-PET scan.
    - iii If the positive FDG-PET at follow-up corresponds to a pre-existing site of disease on CT that is not progressing on the basis of the anatomic images, it is not classified as PD.
- The cytological confirmation of the neoplastic origin of any effusion that appears or worsens during treatment when the measurable tumor has met criteria for response or stable disease is mandatory to differentiate between response or stable disease (an effusion may be a side effect of the treatment) and progressive disease.

• Cytologic and histologic techniques can be used to differentiate between PR and CR in rare cases (e.g., residual lesions in tumor types such as germ cell tumors, where known residual benign tumors can remain.)

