# 11.45 Symptomatic Deterioration

Patients with global deterioration of health status requiring discontinuation of treatment without objective evidence of disease progression at that time, and not either related to study treatment or other medical conditions, should be reported as PD due to "symptomatic deterioration." Every effort should be made to document the objective progression even after discontinuation of treatment due to symptomatic deterioration. A patient is classified as having PD due to "symptomatic deterioration" if any of the following occur that are not either related to study treatment or other medical conditions:

- Weight loss >10% of body weight.
- Worsening of tumor-related symptoms.
- Decline in performance status of >1 level on ECOG scale.

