# Exception: Patients who develop PD in the CNS should discontinue study treatment and go to Event Monitoring.

# **13.3** Criteria for discontinuation of protocol therapy include:

• Disease progression: Where disease progression is: the development of a new metastatic lesion or an objective status of disease progression (as defined by RECIST criteria) on two consecutive evaluations at least 6 weeks apart (Section 13.2).

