# Exception: Patients who develop PD in the CNS should discontinue study treatment.

- Request by patient to discontinue study treatment
- Unacceptable toxicity
- Intercurrent illness that would, in the judgment of the investigator, affect assessments of clinical status to a significant degree or require discontinuation of drug
- Administration of radiotherapy, non-protocol chemotherapy, immunotherapy, biological agents, or an experimental drug during the trial
- Development of new primary cancer
- Ineligibility

Patients who discontinue treatment due to progression or development of a second primary, desire for non-protocol treatment, intolerability, patient request, physician decision, or inter-current illness preventing further administration of protocol treatment will proceed to event monitoring phase of the trial where patient and disease status until death or a maximum of 5 years post-registration

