16.34 Progression-free survival (PFS)

Time from randomization to the first 2 consecutive evaluations approximately 6 weeks apart documenting disease progression. The distribution of progression-free survival times will be estimated using the Kaplan-Meier approach.

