16.35 Overall survival (OS)

Time from registration to death due to any cause. The distribution of overall survival times will be estimated using the Kaplan-Meier approach

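### The PFS definition in 16.34 has no event for death or single-scan CNS progression, no date for a confirmed progression, no censoring rule, and a start point this trial does not have

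*Combined protocol and SAP*

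**What the plan says.** Median PFS is secondary goal 2.22, to be estimated by Kaplan-Meier. The whole definition, in 16.34, is "Time from randomization to the first 2 consecutive evaluations approximately 6 weeks apart documenting disease progression". It does not mention death, censoring, or which of the two evaluations supplies the date. The next section, on overall survival, does name both a start and a death event: "Time from registration to death due to any cause".

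The sections that bear on it are these.

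- **11.1** uses the same two-evaluation rule for the whole protocol: "Disease progression for this protocol is defined as meeting the RECIST criteria for disease progression on two consecutive evaluations at least 6 weeks apart". Its interval is a minimum of 6 weeks, whereas 16.34 says approximately 6 weeks.
- **13.2** makes confirmation the normal path: after a first PD the patient has two more cycles and is re-imaged. The exception that follows removes one group from it: "Patients who develop PD in the CNS should discontinue study treatment and go to Event Monitoring". Section 13.3 repeats the exception.
- **4.1, footnote 8** ties the 6-week scan to staying on treatment: "if a patient has PD yet continues protocol treatment, the next imaging should take place two cycles after the imaging showing PD".
- **13.3** lists other ways to leave: "Patients who discontinue treatment due to progression or development of a second primary, desire for non-protocol treatment, intolerability, patient request, physician decision", among others. These patients go to event monitoring, which 4.2 sets at every 3 months until PD and every 6 months after it, with no imaging listed.
- **11.45** reports as PD "Patients with global deterioration of health status requiring discontinuation of treatment without objective evidence of disease progression at that time", and asks for objective progression to be documented later if possible.
- **11.32** has the only dating rule, for one FDG-PET situation: "In this situation, the date of PD will be the date of the initial abnormal PDG-PET scan".

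**The concern.** An endpoint called progression-free survival should have an event when a patient progresses or dies. The text in 16.34 defines time to confirmed radiographic progression. The protocol itself produces patients who cannot satisfy it (CNS progressors, deaths before confirmation) and others who may not. CNS progression is foreseeable, since 3.29i admits patients with treated, stable brain metastases.

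These are poor outcomes. If such patients are censored, the censoring is informative and the curve is too high. Separately, two analysts could date the same confirmed progressions 6 weeks apart and both comply with the text. With no control arm, neither shift is balanced by a comparator.

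**Working it through.** **The plan's own figure.** The only computed design figure is in 16.2: N=33, one-sided exact binomial, alpha 0.10, 12% against 30%, 90% power. With rejection at 7 or more responses of 33, the exact alpha is 0.0930 and the power 0.9056, so it reproduces. It does not involve PFS. No event count or precision is stated for PFS.

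**Model for size.** The documents give no PFS rate for this population, so I use the 22-week median in 1.2 (95% CI 12 to 36 weeks; pembrolizumab in a different population) as a benchmark only. I assume exponential progression with median m, and scans every 4 cycles of 21 days = 12 weeks (4.1). The chance of progressing within one interval is q = 1 − 2^(−12/m). For m = 22, q = 0.3148.

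**(a) Dating a confirmed PD.** No share has to be assumed. The confirming scan is 2 × 21 = 42 days after the first PD.

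- Dated at the first scan: S(12) = 1 − q = 0.685 and S(24) = 0.685² = 0.469, so the median is 24 weeks.
- Dated at the second scan: the same values fall at weeks 18 and 30, so the median is 30 weeks.

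The shift is 6 weeks whatever m is.

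**(b) One PD only, censored there.** Let a fraction f of progressors have no second PD evaluation and be censored at the only one. Each scan step becomes 1 − q(1 − f), so S(24) = [1 − q(1 − f)]².

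**(c) Deaths censored.** Let a share g of PFS events be deaths, censored when they occur. Each scan step becomes (1 − q)/(1 − qg), so S(24) = [(1 − q)/(1 − qg)]².

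The values of f and g are assumptions. Week 24 is used only to show the height of the curve; it is not a planned endpoint. Event counts are for n = 33, m = 22 and an assumed 104-week cut-off, so the last scan is at week 96: 33 × (1 − 2^(−96/22)) = 31.4, multiplied by (1 − f) or (1 − g).

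| Assumed share | S(24), m=12 | S(24), m=22 | S(24), m=36 | Median, m=22 | Events of 33, m=22 |
|---|---|---|---|---|---|
| none | 25% | 47% | 63% | 24 wk | 31.4 |
| f = 5% | 28% | 49% | 65% | 24 wk | 29.8 |
| f = 10% | 30% | 51% | 66% | 36 wk | 28.3 |
| f = 25% | 39% | 58% | 71% | 36 wk | 23.5 |
| g = 5% | 26% | 48% | 64% | 24 wk | 29.8 |
| g = 10% | 28% | 50% | 66% | 24 or 36 wk | 28.3 |
| g = 20% | 31% | 53% | 69% | 36 wk | 25.1 |

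With 12-week scans the median can move only in 12-week steps. At m = 22 the curve without censoring is at 0.469 at week 24, just below one half, so a small lift moves the median a full step. At g = 10%, S(24) = 0.5005, on the boundary. The direction is firm; the size of a jump is not.

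**Start point.** Section 6.6 requires treatment to begin within 7 days of registration. If randomization were read as start of treatment instead of registration, the clock would differ by at most 7 days.

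**The case against.** Five points can be made for the plan.

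1. *Confirmation is deliberate and is the default.* This stands. Section 13.2 sends a first PD to a confirming scan; 11.1 would accept a later scan; 4.1 has end-of-treatment imaging; 18.5 asks for imaging reports from patients who progress after therapy. A reader might infer that everyone who leaves after one PD is without an event. The documents do not support that: such patients may lack one, because no off-treatment scan is scheduled, but confirmation is possible.
2. *Symptomatic deterioration is already PD.* Section 11.45 says so and asks for later documentation. What is missing is any statement in 16.34 that it counts.
3. *The CNS exception may be meant to waive confirmation.* That is a sensible reading, but the exception concerns stopping treatment, and 16.34 does not adopt it for PFS.
4. *Any analyst would count death.* Perhaps. Deaths are collected under 4.2, and nothing says they will be censored, so a reader should not take censoring as the sponsor's intention. But an explicit definition that omits death, next to an OS definition that names it, should not depend on convention.
5. *The effect sizes are fragile.* Largely true. A reader might compare 24-week PFS under the two dating rules, 69% against 47%, and infer a 22-point bias. Week 24 is itself a scan date. The two curves agree at 68.5% from week 18 to just before 24, and at 46.9% from week 30 to just before 36. The effect on the planned median is 6 weeks.

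**Conclusion.** The definition needs correcting. Followed as written, 16.34 gives time to confirmed progression under the name PFS. It has no event for deaths before confirmation or for CNS progressors without a second scan, and may have none for two further groups. No other section adds death, a general PD date or a censoring rule.

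The firm size is the dating gap: about 6 weeks per confirmed PD and in the median (24 against 30 weeks on the benchmark, which comes from a different population). Overstatement from missing events is conditional on those patients being censored, and on shares the documents do not give. At assumed shares of 5% to 10% for either group, the benchmark curve at week 24 rises by about 2 to 4 points. Larger figures need larger assumed shares.

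PFS is secondary and descriptive, with no test attached. It would be wrong to infer that the trial's main conclusion is at risk: the response rate, its test and N=33 do not use 16.34. The word randomization is a slip with at most a few days' effect.

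**What to change.** Replace 16.34 with:

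> PFS is the time from registration to the earliest of: confirmed PD, dated at the first of the two consecutive PD evaluations; CNS PD, which needs no confirmation and is dated at that evaluation; PD due to symptomatic deterioration (11.45); or death from any cause. Patients without an event are censored at the last disease evaluation.

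Add a sensitivity analysis that counts a first non-CNS PD with no later scan as an event on its own date. Making that the main rule is also defensible, but it departs from the two-evaluation rule in 11.1 and would need a matching exception there. The same paragraph should give the date used for symptomatic deterioration, and say how new anticancer therapy before PD and a missed confirming scan are handled; the wording above does not settle these.

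The cost is one paragraph, settled before the data are analysed. No scan, visit or patient is added, because progression and death are already collected under 4.2. The reported PFS may be slightly less favourable.

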16.35 Overall survival (OS)

Time from registration to death due to any cause. The distribution of overall survival times will be estimated using the Kaplan-Meier approach

# 16.4 Correlative endpoints

A time series plot of individual patient TILs will be constructed. Also, the change in the number of tumor infiltrating lymphocytes (TILs) in tumor biopsies taken prior to and following cryoablation and intra-tumoral mDCs on Cycle 2 and on Cycle 3 will be determined. For a given cycle, the percent change in the number of TILs following cryoablation and intra-tumoral mDCs from pre- cryoablation and intra-tumoral mDCs levels will be determined.

A times series plot of individual patient PD-L1 levels found in tumor biopsies as well as blood biopsies will be constructed and visually assess for trends within and between biopsy types. Wilcoxon rank sum tests will be used to assess whether the amount of the change in PD-L1 levels after first cryoablation and intra-tumor or the PD-L1 levels at completion of second cryoablation and intra-tumor differ among those patients who met the criteria for clinical benefit (progression-free and on study for at least 6 months) and those who do not.

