# 1.2 Pembrolizumab for advanced melanoma

Pembrolizumab is a human IgG4 PD-1 blocking antibody that is recently approved by the FDA for the treatment of patients with unresectable or metastatic melanoma and disease, including progression following ipilimumab and, if BRAF V600 mutation positive, a BRAF inhibitor. Pembrolizumab showed an unprecedented rate of durable clinical responses, with an overall response rate of 26% and median progression-free survival of 22 weeks (95% CI: 12-36 weeks). Treatment has generally been well-tolerated, and the most common drug-related adverse events (AEs) of any grade were fatigue (33%), pruritus (26%), and rash (18%). Patients responding to treatment showed proliferation of CD8 T cells in their tumors.

Despite the promising data associated with pembrolizumab treatment, the majority of melanoma patients do not respond to pembrolizumab. Several possible mechanisms for pembrolizumab (and other PD-1 blockade) resistance exist, including additional mechanisms of immunosuppression in the tumor microenvironment and derangements in systemic immune competence. The evaluation of melanoma gene expression revealed that tumors infiltrated with CD8+ T cells also

showed expression of a type I interferon transcriptional signature.  Interferon gamma (IFN $\gamma$ ) has the capacity to increase MHC-dependent antigen presentation in a variety of cell populations, including transformed melanocytes both in vitro and in vivo, and is produced in response to T cell recognition of tumor-associated antigens. IFN $\gamma$  also causes many tumor cells to upregulate PD-L1, suggesting that an ongoing T cell response in which IFN $\gamma$  is produced may prime tumors to benefit from anti-PD-1 therapy. Conversely, tumors with few tumor-related T cells have minimal IFN $\gamma$  and are unlikely to benefit from PD-1-based therapies.

The failure of the immune system to recognize and eradicate cancer cells may partly be a result of insufficient immunological activation. One potential hurdle to benefit from anti-PD-1 therapy is a lack expanded tumor-related T cells. As such, there is strong rationale for combining a strategy to expand melanoma-specific tumor-infiltrating lymphocytes (TILs) with pembrolizumab.

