# 2.3 Translational

- 2.31 To quantitate tumor infiltrating lymphocytes (TILs) in tumor biopsies prior to and following cryoablation and intratumoral mDCs.
- 2.32 To measure PD-L1 levels in tumor biopsies and blood biopsies prior to and following cryoablation and to assess whether a change in PD-L1 levels differ among those patients who met the criteria for clinical benefit (progression-free and on study for at least 6 months) and those who do not.
- 2.33 To measure peripheral blood mononuclear cells (PBMC) proliferation and function after coculture with frozen tumor before and after intratumoral mDC injection.

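### The second PD-L1 test in Section 16.4 compares raw levels, while objective 2.32 asks about change, so a pre-existing difference between the benefit groups could be read as treatment-related

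*Combined protocol and SAP*

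**What the plan says.** Section 2.3, objective 2.32, measures PD-L1 in tumor and blood before and after cryoablation and sets one inferential question: "to assess whether a change in PD-L1 levels differ among those patients who met the criteria for clinical benefit".

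Section 16.4 gives the analysis. Individual PD-L1 series are plotted and inspected by eye. Then "Wilcoxon rank sum tests will be used to assess whether" either of two quantities differs by clinical benefit. The first is "the amount of the change in PD-L1 levels after first cryoablation". The second is whether "the PD-L1 levels at completion of second cryoablation and intra-tumor differ among those patients who met the criteria for clinical benefit". The grouping is by clinical benefit: "progression-free and on study for at least 6 months) and those who do not".

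No subtraction, percent change or baseline adjustment is attached to the second quantity. For TILs, the same section does define a percent change from the pre-cryoablation value in each cycle.

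The notes to the test schedule in Section 4.1 fix the samples. For tissue: "Tumor biopsies will be performed immediately prior to cryoablation on Cycle 2 Day 1 or 2 and Cycle 3 Day 1 or 2", and later "Tumor biopsies will be performed at the end of Cycle 4 after radiologic evaluation". Immune-monitoring blood is drawn before each of Cycles 1 to 5. Section 7.5 has two different lesions ablated, one in Cycle 2 and the other in Cycle 3.

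**The concern.** A post-treatment level contains whatever PD-L1 the patient had beforehand. Clinical benefit is an outcome, not a randomised assignment, so the two groups may differ in PD-L1 before any cryoablation or dendritic-cell injection. Section 1.2 makes this plausible. It notes that IFN-gamma "causes many tumor cells to upregulate PD-L1, suggesting that an ongoing T cell response in which" it is produced may prime tumors to benefit from anti-PD-1 therapy.

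If the groups start apart and change by the same amount, a rank-sum test on the final level can be significant although the answer to 2.32 is no. If the benefit group starts lower and rises more, the level test can miss a difference in change that 2.32 was written to find.

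**Working it through.** **The plan's own figure.** The only sizing in the documents is for the primary endpoint (Section 16.2): 33 patients, 12% versus 30%, one-sided exact binomial at 0.10, 90% power. It reproduces: rejecting at 7 or more responses of 33 gives alpha 0.0930 and power 0.9056. No alpha, sidedness, power or PD-L1 distribution is stated for the PD-L1 tests, so everything below rests on assumptions.

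**Assumed inputs.** 33 patients split 11 with benefit and 22 without; two-sided 0.05; normal data with baseline SD 1; baseline difference d = 0.5 to 1.0 SD; pre/post correlation r = 0.5 to 0.7.

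**Models for the post-treatment value:**
- A. Baseline plus independent noise, equal change in both groups. The post-treatment SD is 1/r.
- B. Equal variances before and after, equal change in both groups.
- C. r times baseline plus noise, equal variances, no group effect given baseline (regression to the mean).

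**Size of the distortion.** The standardised group difference seen by each test is:

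| Model | Level test | Change test |
|---|---|---|
| A | d × r = 0.25 to 0.70 | 0 |
| B | d = 0.50 to 1.00 | 0 |
| C | d × r = 0.25 to 0.70 | d × √((1 − r)/2) = 0.19 to 0.50, opposite sign |

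**Approximate rejection rate.** For the rank-sum test, multiply the standardised difference by k = √(11 × 22/33) × √(3/π) = 2.708 × 0.977 = 2.65, and take P(Z > 1.96 − kδ) + P(Z < −1.96 − kδ).
- δ = 0.25: kδ = 0.66, about 10%
- δ = 0.70: kδ = 1.85, about 46%
- δ = 0.50: kδ = 1.32, about 26%
- δ = 1.00: kδ = 2.65, about 75%

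**Simulated rejection rates**, which these approximations match to within a few points:

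| Model | Level test | Change test |
|---|---|---|
| A | 9-44% | about 5% |
| B | 25-72% | about 5% |
| C | 8-42% | 7-26% |

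In C, a rank comparison of the post-treatment value adjusted for baseline holds about 5%.

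**Sensitivity to the split.** Under model B with 7, 10 or 16 of 33 patients benefiting and r = 0.3 or 0.7, the level test rejects in 4-5% of trials at d = 0, 20-28% at d = 0.5 and 58-78% at d = 1.0. The change test stays near 5%.

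**The opposite error.** Let the benefit group start 1 SD lower and truly rise 1 SD more (r = 0.7, 10 or 16 benefiting). The level difference is −1 + 1 = 0, so the level test rejects in about 5% of trials. The change test rejects in 89-94%.

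**The case against.** **The first comparison already tests a change.** This stands. It would be wrong to infer that 2.32 has no matching analysis. The gap concerns the second comparison, which covers the period after both procedures.

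**The phrase about the amount of change might govern both items.** The grammar allows it. The second item has its own noun phrase, so the level reading is the natural one. If change was meant, the reference sample is still unnamed.

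**A level comparison has a legitimate use.** Section 17.21 lists PD-L1 expression among exploratory biomarkers to predict response. For that question a difference in level is a valid finding, and nothing in 16.4 says the level test measures a treatment effect. So the comparison may stay under its own label, but it does not answer 2.32.

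**The patient plots would show imbalance.** They may, but visual inspection does not adjust a test.

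**Section 1.2 does not predict a baseline difference here.** This also stands. A reader might infer that the groups are expected to differ at the outset. The text says only that a T-cell response may prime tumors, as general background on anti-PD-1 therapy. This trial enrols patients whose disease did not respond to, or progressed on, PD-1 or PD-L1 therapy (criterion 3.13).

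**A change score is not safe in general.** Correct. Models A and B hold the change test at 5% by construction, and under C it is off as well. At r = 0.1 and d = 1 under C, the change test rejects in 41% of trials and the level test in 6%. Baseline adjustment is not safe in every model either: under B the group difference given baseline is d − rd = d(1 − r), which is not zero. Change and adjusted analyses answer different questions, so both should be reported.

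**Tumor change may mix lesions.** Correct. Two lesions are ablated, and Section 4.1 does not say which is biopsied at the end of Cycle 4.

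**Conclusion.** The point holds in a limited form. As worded, the second rank-sum test in 16.4 compares raw levels between groups formed by outcome and cannot separate a pre-existing PD-L1 difference from a treatment-related one. With a true baseline difference of 0.5 to 1.0 SD, the level test would be significant in roughly 9% to 72% of trials with equal change, depending on the variance model, and it could also miss a real difference in change. These rates depend on assumed values for the baseline difference, correlation, group split and alpha.

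The documents do not support saying that the groups will differ at baseline, or that the level test will be reported as a treatment effect. Both are possibilities that the wording leaves open. This is a translational objective; the primary endpoint and N = 33 are untouched.

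**What to change.** In Section 16.4:

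1. Define the second comparison as the change from the pre-cryoablation sample (pre-Cycle 2) to the sample after the second cryoablation (end of Cycle 4 biopsy; blood before Cycle 5), by rank-sum test, separately for blood and tumor.
2. Add as sensitivity a rank-based comparison of the post-treatment value adjusted for the pre-Cycle 2 value, because an unadjusted change score is affected by regression to the mean.
3. For tumor, record which lesion each biopsy comes from. Compute the change within the same lesion where possible; otherwise label it a between-lesion comparison.
4. State that the pre-Cycle 2 sample follows Cycle 1 pembrolizumab and is therefore not a baseline free of protocol treatment. For blood, the pre-Cycle 1 draw can also serve as reference.
5. If the raw-level comparison is kept, label it a separate exploratory biomarker analysis that does not answer 2.32.

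**Cost:** a few sentences in 16.4, a lesion identifier for each biopsy, slightly more analysis, and the loss of patients without paired samples from the change comparison. No new specimens are needed.
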